1. LIST OF ABBREVIATIONS

AAA	Abdominal aortic aneurysm
IAA	Iliac arterial aneurysms
FAA	Femoral arterial aneurysms
PAA	Popliteal arterial aneurysms
ADE	Adverse Device Effect
AE	Adverse Event
ABI	Ankle Brachial Index
AD	Aortic Dissection
CLTI	Chronic limb-threatening ischemia
MI	Myocardial Infarction
PAD	Peripheral arterial disease
PMCF	Post-Market Clinical Follow-up
SADE	Serious Adverse Device Effect
TASC	Trans-Atlantic Inter-Society Consensus
USADE	Unanticipated Serious Adverse Device Effect
aTAA	Ascending Thoracic aortic Aneurysm
dTAA	Descending Thoracic Aortic Aneurysm

PROTOCOL	2021-PT-01
TITLE:	Safety and Performance of POLYTHESE® vascular prosthesis
EFFECTIVE DATE:	1 July 2021

2. SYNOPSIS

Title:	A Retrospective, Observational, Multicenter, Study to Collect Clinical Safety and Performance data on POLYTHESE® vascular prostheses
Study Population :	Subjects who did receive POLYTHESE® at least one year ago for replacement or bypass of pathological arteries. 3 main sub-populations will be studied depending on location of surgery (thoracic or abdominal and peripheral), but data will be collected for all subjects who did receive POLYTHESE® vascular prosthesis.
Study Design:	Multi-center retrospective case series
Study Type:	PMCF
Number of subjects:	Data from a minimum of 300 subjects will be evaluated. A minimum of 200 subjects will be evaluated for thoracic location of surgery.
Follow-up	At least 1-year follow-up after surgery until a maximum of 5 years.
Study Product:	Any POLYTHESE® vascular prosthesis of following ranges: 
 - POLYTHESE® IC - POLYTHESE® ICT - POLYTHESE® IC-3GL
Intended use:	POLYTHESE® vascular prostheses are indicated for replacement or bypass of arteries presenting aneurysm or arterial disease. Their indication is restricted to thoracic, abdominal and peripheral surgery not involving the crossing of the knee flexion crease.
Objectives:	
 • Describing safety and performance of POLYTHESE® throughout its expected lifetime
Performance primary endpoint:	Primary patency rate at 1 year after surgery using POLYTHESE®
Safety Primary endpoints:	
 • Mortality rate at 30 days after surgery using POLYTHESE®
Performance secondary endpoints:	
 • Procedural success rate • Primary patency rate at 30 days and 6 months after surgery using POLYTHESE® • Primary assisted patency rate at 30 days, 6 months and 1 year after surgery using POLYTHESE® • Secondary patency rate at 30 days, 6 months and 1 year after surgery using POLYTHESE®

PROTOCOL	2021-PT-01
TITLE:	Safety and Performance of POLYTHESE® vascular prosthesis
EFFECTIVE DATE:	1 July 2021
	
 • Device failure during procedure or at discharge, at 30 days, 6 months and 1 year after surgery using POLYTHESE®
Safety secondary endpoints	
 • Mortality rate during procedure or at discharge, at 6 months and 1 year after surgery using POLYTHESE® • Limb salvage rate at 30 days, 6 months and 1 year after surgery using POLYTHESE® • Adverse event during procedure or at discharge, at 30 days, 6 months and 1 year after surgery using POLYTHESE®
Exploratory endpoints	
 • After 1 year until the end of follow-up (5 years) using POLYTHESE®: 
 ○ Primary patency ○ Primary assisted patency ○ Secondary patency ○ Device failure ○ Mortality ○ Limb salvage ○ Adverse events ○ Identify possible systematic misuse or off-label use of POLYTHESE®, with a view to verifying that the intended clinical purpose is correct.
Inclusion criteria	Subjects who did receive POLYTHESE® (IC, ICT, IC-3GL) at least one year ago for replacement or bypass of arteries presenting aneurysm or arterial disease
Exclusion criteria	Patients who have objected to the collect of their data
Duration of the data collect:	6 months from first site operational to collect data until data delivery
Data to be collected (as far as available)	
 • Identification and demographic data 
 ○ Patient characteristics ○ Indication and location of surgery ○ Patients demographics and risk factors ○ Summary of previous cardiovascular interventions ○ Relevant medications ○ Diagnosis • Operative data 
 ○ Date of procedure

PROTOCOL	2021-PT-01
TITLE:	Safety and Performance of POLYTHESE® vascular prosthesis
EFFECTIVE DATE:	1 July 2021

- Identification data for the prosthesis
- Information related to the surgical procedure
- Relevant medication
- Assessment of prosthesis function and mode of assessment if available
- Device failure modes and documented adverse operative events

- **Post-operative data (follow-up)**

- Date of follow-up visits
- Summary of vascular interventions, including minimally invasive procedures
- Clinical evaluation
- Relevant medications
- Device failure modes and documented adverse events

- **Any documented adverse events data (as far as available)**

- Type of event, date of occurrence, severity, management, outcome
- Any Documentation of probable causative factors (e.g. caused by the prosthesis, patient factors, technical factors)

Timepoints of collected data	- During procedure and at discharge (7-14 days)
	- 30-days after surgery ('peri-operative')
	- 6, 12 months
	- Annually up to 5 years post procedure

3. INTRODUCTION.

POLYTHESE® IC and ICT devices are CE-marked and were initially introduced in the international market in 1997, followed in 2003 and 2005 respectively by POLYTHESE® and POLYTHESE® devices. POLYTHESE® IC-3GL devices were then introduced in 2009.

Since January 2002, more than 60 000 single devices have been sold across various markets worldwide.

PROTOCOL	2021-PT-01
TITLE:	Safety and Performance of POLYTHESE® vascular prosthesis
EFFECTIVE DATE:	1 July 2021

4. STUDY DEVICE

The studied device is POLYTHESE®, which consists in uniform straight or bifurcated tubular synthetic textile coated vascular grafts.

POLYTHESE® vascular prostheses are made by weaving of polyethylene terephthalate (PET – polyester) yarns and impregnated with collagen CXE® coating of bovine origin.

CXE® collagen impregnation of the POLYTHESE® vascular prostheses ensure water permeability of less than 10 ml/cm²/min at a pressure of 120 mm of mercury (Hg) and allows direct implantation of the prosthesis without the need for pre-clotting.

4.1. Summary description of the device

The POLYTHESE® vascular prostheses are divided into 3 different ranges according to their configuration:

- POLYTHESE® IC

POLYTHESE® IC are straight tubes or bifurcated prostheses (*Figure 1*), with nominal diameters ranging from 6 to 28 mm, and usable length from 15cm to 100 cm.

- POLYTHESE® ICT

POLYTHESE® ICT are straight tubes with two equidistant longitudinal black guidelines over the entire length (*Figure 1*), with nominal diameters ranging from 30 to 38 mm, and usable length from 15cm to 60 cm.

- POLYTHESE® IC-3GL

POLYTHESE® IC-3GL are straight tubes with three equidistant longitudinal black guidelines over the entire length (*Figure 1*), with nominal diameters ranging from 20 to 38 mm, and usable length from 15cm to 60 cm.

A wide range of dimensions / references is available for each device listed in Appendix.

Figure 1: POLYTHESE® IC/ICT and POLYTHESE® IC-3GL vascular grafts

PROTOCOL	2021-PT-01
TITLE:	Safety and Performance of POLYTHESE® vascular prosthesis
EFFECTIVE DATE:	1 July 2021

4.2. Intended purpose and patient population

4.2.1. Intended clinical purpose

POLYTHESE® IC, ICT and IC-3GL vascular prostheses ranges are indicated for replacement or bypass of arteries presenting aneurysm or arterial disease. Their indication is restricted to thoracic (POLYTHESE® ICT), abdominal and peripheral surgery not crossing the knee flexion crease.

POLYTHESE® IC-3GL prostheses are especially indicated in aortic root and ascending thoracic aorta surgery.

4.2.2. Patient population characteristics

Patient population conditions that may indicate abdominal, thoracic and/or peripheral vascular open surgical repair with implantation of a vascular graft include:

- Peripheral arterial diseases (PAD), characterized by reduced blood flow to the lower extremities, which may be categorized as:
 - Intermittent claudication (IC)
 - Chronic limb-threatening ischemia (CLTI)
 - Acute limb ischemia (ALI)
 - Chronic total occlusion (CTO)
- Arterial aneurysms, characterized by a permanent localized (i.e., focal) dilatation having at least a 50% increase in diameter, which may be categorized by location:
 - Thoracic aortic aneurysm (TAA)
 - Ascending thoracic aortic aneurysm
 - Aortic arch thoracic aortic aneurysm
 - Descending thoracic aortic aneurysm
 - Thoraco-abdominal aortic aneurysm
 - Thoracic aortic aneurysms
 - Ascending aorta
 - Descending thoracic aorta
 - Abdominal aortic aneurysms (AAA)
 - Peripheral arterial aneurysms
 - Iliac arterial aneurysms (IAA)
 - Femoral arterial aneurysms (FAA)
 - Popliteal arterial aneurysms (PAA)
- Arterial dissections are classified according to the location of the entry intimal tear and the extent of aorta involved in the dissection:
 - Stanford type A dissection
 - Type I Dissection (originates in the ascending aorta, extends through the aortic arch, and continues into the descending aorta and/or abdominal aorta).
 - Type II Dissection (originates in and is confined to the ascending aorta)

PROTOCOL	2021-PT-01
TITLE:	Safety and Performance of POLYTHESE® vascular prosthesis
EFFECTIVE DATE:	1 July 2021

- Stanford type B dissection
 - Type IIIa Dissection (originates in the descending aorta and is limited to same)
 - Type IIIb Dissection (involves descending and variable extents of the abdominal aorta)
- Connective tissues abnormalities such as in Marfan Syndrome, Ehler-Danlos Syndrome, annulo-ectasia disease, hereditary dysplasia, conjunctival elastic and media dystrophies

4.2.2.1. Peripheral arterial diseases (PAD)

Reported PAD risks factors are:

- History of cardiovascular disease
- Smoking
- Diabetes mellitus
- Hypertension
- Dyslipidemia
- Obesity
- Age

Age is the strongest risk factor for PAD. The disease is rare in individuals younger than 40 years, rises in prevalence in the sixth to eighth decades, and may affect 25% or more of individuals 80 years and older.

4.2.2.2. Arterial aneurysms

Reported arterial aneurysms risks factors are:

- advanced age,
- gender,
- smoking,
- family history,
- obesity,
- hypertension,
- co-morbidities such as coronary heart disease, diabetes, atherosclerosis.

Although abdominal aortic aneurysms (AAAs) and ascending aortic aneurysms are more common, descending thoracic aortic aneurysms (TAAs) and thoracoabdominal aortic aneurysms (TAAAs) are not rare, with an estimated incidence of around 10 cases per 100,000 person-years.

TAAAs are primarily a disease of the elderly. The average age of patients with TAAAs is 65 years, with a male-female ratio of 1.7 : 1. TAAAs clearly have a genetic component, since more than 20% of patients will have a first-degree relative affected by aneurysm disease.

Aneurysms involving the aortic arch account for about 10% of the total cases of thoracic aorta aneurysms.

PROTOCOL	2021-PT-01
TITLE:	Safety and Performance of POLYTHESE® vascular prosthesis
EFFECTIVE DATE:	1 July 2021

Prevalence of abdominal aortic aneurysms (AAA) 4 cm or larger is approximately 1% of men between the ages of 55 and 64 years and increases with advancing age by 2% to 4% by decade. Emergence of AAAs rises sharply in individuals aged ≥ 60 years old. It has also been consistently demonstrated that AAAs occur with greater frequency in men, smokers, and those with a family history of aortic aneurysm.

Data on prevalence of AAA varies between 1.3% and 12.5% in males, and between 0.0% and 5.2% in females. Overall prevalence varies from 4 to 8%.

Iliac artery aneurysms (IAAs) commonly occur concurrently with other more proximal arterial aneurysms. In contrast to generalized aorto-iliac aneurysms, isolated iliac aneurysms are prevalent in $\leq 2\%$ of the general population.

Femoral artery true aneurysms are found predominantly in older men (70 years or older) and are associated with smoking and hypertension.

Popliteal artery aneurysms are rare in the general populations, although they are the most common peripheral artery aneurysms (70% of them). PAAs are exclusively found in men. A prevalence of around 1% in men has been reported in UK between 65 and 85 years.

4.2.2.3. Aortic dissections

Factors that predispose one to develop aortic dissection include:

- age,
- hypertension,
- structural abnormalities of the aortic wall

Incidence of acute aortic dissection ranges from 2 to 4 per 100,000 person-years. The incidence of type A dissection peaks between 50 and 60 years, while type B dissections occur more frequently between 60 and 70 years of age.

4.2.2.4. Connective tissue abnormalities including Marfan syndrome, Ehler-Danlos Syndrome, conjunctival elastic and media disorders

A connective tissue disease is a genetic disease in which the primary target is either collagen or elastin protein assembly, disruption of which leads to an inherent predisposition to degeneration, loss of structural integrity, and consequent aneurysm formation or spontaneous vascular dissection and rupture. These connective tissue abnormalities have severe vascular manifestations, and most commonly include Marfan syndrome (MFS), the vascular type of Ehlers-Danlos syndrome (EDS IV), Loays-Dietz syndrome (LDS), and familial thoracic aortic aneurysm and dissection.

The vascular manifestations of Marfan syndrome invariably involve aortic root dilation, progressive root and ascending aortic aneurysmal degeneration, and potentially aortic dissection of variable extent. The incidence of Marfan syndrome (MFS) is about 2 to 3 per 10,000 individuals, with no gender predisposition. This genetic disorder is a dominant Mendelian trait in 75% of cases.

The prevalence of Ehler-Danlos Syndrome (EDS), with type III procollagen disorder, is currently estimated to be 1 in 50,000 to 90,000. Major complications in childhood are rare, even if 25% of the

PROTOCOL	2021-PT-01
TITLE:	Safety and Performance of POLYTHESE® vascular prosthesis
EFFECTIVE DATE:	1 July 2021

subjects may present medical or surgical complications by the age of 20. By 40 years of age, major complications in the vascular or gastrointestinal systems or reproductive system (women) had developed in around 90 %.

4.3. Contra-indications

The use of any model of POLYTHESE® vascular prostheses is contra-indicated for:

- Coronary bypasses
- Patients with hypersensitivity to collagen

5. STUDY DESIGN

POLYTHESE® study is a retrospective, observational, multicentre, case series which examine short and long-term outcomes of using POLYTHESE®. This study will be done on Real World Data to describe the safety and performance of the device.

which used reversed vein and 52 of which used 6-mm **POLYTHESE® IC collagen prosthesis**. When collagen prosthesis was used, operating time was shorter than vein bypass graft (73±9.1 minutes vs. 105±8.8 minutes, $p=0.002$). Two cases with collagen prosthesis had superficial wound infection which did not require reoperation and result in graft loss. None of the patients who had collagen prosthesis were lost to follow-up. Primary patency rates of collagen prosthesis vs. vein bypass graft were 67% vs. 81% ($p=0.065$) at 2-year. After reintervention, the secondary patency rates of autogenous grafts vs collagen prosthesis were 81% vs. 77% ($p=0.298$) at 3-year. The difference between collagen prosthesis and bypass graft in terms of patency rates were not statistically significant due to short follow-up time and longer time is required to see a significant difference. Nevertheless, results suggest that collagen prosthesis can be safely used for femoropopliteal bypass grafting.

Prospective non-randomized single-centre study (published data)

A prospective non-randomized single-centre study [Benetis 2014] was performed to compare the outcome of stent and surgery in terms of treatment success. Of 316 patients who underwent angiography, 101 consecutive patients treated for TASC II type B, C, and D iliac lesions were divided into two groups: (i) 54 patients (stent group) who underwent iliac endovascular procedures and (ii) 47 patients (surgery group) who underwent direct aortoiliac bypass reconstructions. All patients were followed up to assess the early, 1-year and 2-year stent and graft patency. Patients who underwent direct aortoiliac bypass reconstruction underwent either bilateral ($n=7$) or unilateral bypass ($n=40$) reconstruction, and collagen coated **POLYTHESE® IC** prostheses were used for bilateral reconstructions. Overall, 1- and 2-year prosthetic graft patencies were 97.1±2.9% and 97.1±2.9%, respectively. No perioperative mortality was observed in either of the groups. In the surgery group, 2 patients were lost to myocardial infarction (MI), one after 14 months and the other after 19 months following the surgery. Assisted primary patency rates of the surgery group were higher than the stent group. Complication rate was 7.4% in the stent group whereas it was 6.3% in the surgery group, which included pneumonia, wound complications and inguinal lymphorrhoea. Neither graft infection nor early mortality were observed in the surgery group, although this was attributed to the small number of patients undergoing above-knee femoropopliteal bypass procedures ($n=7$). In conclusion, both stent and grafting were found to be safe procedures for patients with severe aortoiliac occlusive disease.

Clinical non-comparative study

Kaplan et al. (2015) conducted a clinical non-comparative study with the aim to report the outcomes of patients who underwent proximal thoracic aortic aneurysm surgery with open distal anastomosis technique but without cerebral perfusion, instead under deep hypothermic circulatory arrest. A total of 30 patients (21 male, 9 female) with an average age was 60.2 ± 11.7 years (range, 30-74 years), with ascending aorta aneurysm associated with aortic valvular disease, coronary artery disease, or mitral valve disease were included. During this study, 12 patients were implanted with **POLYTHESE®** for proximal thoracic aortic aneurysm repair (other types of grafts were implanted).

5.2. Rationale for PMCF study

Available evidence confirms acceptability of performance and side effects related to POLYTHESE®; however, intended claims on clinical safety and performance are not sufficiently supported with existing clinical evidence, especially for long term assessment and thoracic use. In order to keep POLYTHESE® in European market, a post-market clinical follow-up (PMCF) study is needed.

5.3. Subjects

The participating hospitals will screen all potential subjects and will select those who are appropriate for study inclusion, i.e. subjects implanted with POLYTHESE® for at least one year, or with complete data to death. As the study explores real world data, there is no exclusion criteria for subjects and all subjects with POLYTHESE® implanted for at least one year and have not objected to the collect of their data will be included in the study.

All data will be retrieved from medical charts for each patient from time of surgery (considered as index date) until a maximum of 5 years after surgery.

Data from a minimum of 300 from 3 to 8 different sites in France will be evaluated. A minimum of 200 subjects with thoracic location of surgery will be evaluated.

Not more than 50% of study total enrolled subjects shall pertain to one unique centre.

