5.3.1. Inclusion criteria

Patients must meet the following inclusion criteria in order to be eligible for inclusion in the study:

- Patient has a minimum of 1-year post-operative follow-up data available, or complete data to death

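### The synopsis and sections 5.3/5.3.1 disagree on whether the one-year surgery-date limit covers patients who died; if it does not, 30-day mortality is biased upward

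*Protocol*

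**What the plan says.** The eligibility rule appears in three places in the protocol.

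- **Synopsis.** The study population is "Subjects who did receive POLYTHESE® at least one year ago for replacement or bypass of pathological arteries". The inclusion row repeats the limit: "Subjects who did receive POLYTHESE® (IC, ICT, IC-3GL) at least one year ago for replacement or bypass of arteries presenting aneurysm or arterial disease". Neither row provides an alternative for patients who died.
- **Section 5.3.** Sites select "subjects implanted with POLYTHESE® for at least one year, or with complete data to death". The next sentence does not mention death; it reads, in part: "all subjects with POLYTHESE® implanted for at least one year and have not objected to the collect of their data will be included in the".
- **Section 5.3.1.** The single listed criterion is "Patient has a minimum of 1-year post-operative follow-up data available, or complete data to death". It is a condition on available data and contains no surgery date.

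Section 5.3.2 excludes only patients who objected to data collection. Charts are read "from time of surgery (considered as index date) until a maximum of 5 years after surgery". That caps follow-up but sets no calendar window for the operations. The primary safety endpoint is "Mortality rate at 30 days after surgery using POLYTHESE"; mortality at discharge, six months and one year is secondary.

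**The concern.** The death alternative in 5.3 and 5.3.1 has no surgery-date condition. Take two patients operated on the same day, three months before a site extracts its data. One died on day 10 and has a complete file, so meets the wording of both sections. The other is alive, cannot have one year of implantation or follow-up, and cannot be included. Under the synopsis neither qualifies.

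On the wording of 5.3 and 5.3.1, then, the entry window is one year longer for the dead than for the living. The last year of operations adds deaths to the numerator and adds nobody but those who died to the denominator. Complete follow-up does not remove this, and neither does a larger sample. Because the study is descriptive, the reported rate is itself the result. Sites that follow different passages, or review different numbers of years, would also report rates that are not comparable.

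**Working it through.** **No plan figure to reproduce.** The protocol gives no expected mortality, no surgery window and no yearly volume. Its 300 subjects (200 thoracic) are justified by feasibility alone. The inputs below are therefore assumptions, apart from the low anchor noted further down.

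**Model.** Yearly volume is constant and follow-up is perfect. W is the number of eligible years of surgery (at least one year before extraction), m is true 30-day mortality, and d is the share of the last year's patients dead at extraction. Per unit of yearly volume, under the literal wording of 5.3/5.3.1:

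- 30-day deaths counted: W·m + m
- subjects counted: W + d
- reported rate = (W·m + m)/(W + d)

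Dividing by m gives (W + 1)/(W + d). With f = 1/(W + 1), this is just under 1/(1−f) = (W + 1)/W.

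| Eligible years W | 1/(1−f) | m = 5%, d = 7% | m = 10%, d = 12% |
|---|---|---|---|
| 1 | 2.00 | 0.10/1.07 = 9.3% | 0.20/1.12 = 17.9% |
| 3 | 1.33 | 0.20/3.07 = 6.5% | 0.40/3.12 = 12.8% |
| 5 | 1.20 | 0.30/5.07 = 5.9% | 0.60/5.12 = 11.7% |
| 10 | 1.10 | 0.55/10.07 = 5.5% | 1.10/10.12 = 10.9% |

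**Finer check.** The formula credits the last year with all its 30-day deaths, although patients operated on in the final month have not completed 30 days. A second calculation spreads deaths evenly over days 0–30 and then over day 30 to one year, with one-year mortality of 10% (for m = 5%) or 15% (for m = 10%). With six years of surgery in all (five eligible) it gives 5.9% and 11.6%. With two years in all (one eligible) it gives 9.2% and 17.5%. The simple formula overstates slightly.

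**Low end.** Section 5.1 reports one hospital death in 30 patients (3.3%) in a series where 12 received the device. Taking 3.3% as true 30-day mortality and 6% at one year, the finer calculation gives 3.9% with six years in all.

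**One-year mortality.** With a true value of 10% and d = 7%, the reported proportion is (5 × 0.10 + 0.07)/5.07 = 0.57/5.07 = 11.2% for five eligible years, and 0.37/3.07 = 12.1% for three. The relative inflation is smaller than at 30 days because the last year's deaths are incomplete at one year.

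**Against sampling error.** At 5% and n = 300 the 95% half-width is 1.96 × √(0.05 × 0.95/300) = 2.5 points. The shift is 0.9 points for five eligible years and 1.5 for three. In the single-eligible-year case it is about 4 points, which exceeds the half-width.

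**Under the synopsis rule.** If surgery at least one year ago is required of everyone, the last-year terms vanish: W·m/W = m, a ratio of 1.00.

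**The case against.** The strongest reply is that the protocol, read as a whole, already applies the limit to everyone. It appears twice in the synopsis, and the second sentence of 5.3 again speaks only of subjects implanted for at least a year. The death clause also has a legitimate purpose: without it, a patient operated on long ago who died before one year could never supply one-year data, and early deaths would be lost. Section 5.3.1 fits this reading, since the alternative there is to a data requirement and not to a surgery date.

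Much of this stands. A reader might infer that the protocol has settled on a longer entry window for deaths, so that 30-day mortality is certainly inflated. The documents do not support that. The excess appears only where a site uses 5.3/5.3.1 without the synopsis limit. A reader might also infer that the size depends only on the number of years reviewed; it depends as well on mortality, the share dead at extraction and the volume trend.

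It is also fair that the shift is modest for multi-year windows, that no hypothesis is tested, and that the error would overstate the risk of the device. A single eligible year is an unlikely case for a study that follows patients for up to five years.

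What remains is that 5.3.1 is the list patients must meet, and neither it nor 5.3 says that the death clause excuses only the data requirement. The second sentence of 5.3 says who will be included; it does not withdraw the alternative offered in the sentence before.

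**Conclusion.** The passages conflict, and the conflict bears on the primary safety endpoint. If 5.3 and 5.3.1 are applied as worded, 30-day mortality is inflated by roughly 1/(1−f), slightly less in practice. An assumed 5% becomes about 5.9% with five eligible years and 6.5% with three; an assumed 10% becomes 11.7% and 12.8%. One-year mortality is also raised, by a smaller factor. If the synopsis limit governs, this bias is absent.

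The figures rest on constant yearly volume, perfect follow-up and assumed mortality. For windows of several years the shift at 5% is about one point, inside the 2.5-point half-width at n = 300. The point deserves correction because the bias is systematic and upward and costs almost nothing to remove, not because it is shown to be large.

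**What to change.** Reconcile the synopsis, 5.3 and 5.3.1. State in 5.3 and 5.3.1 that the date of surgery must be at least 12 months before the site's data-extraction date, for living and deceased subjects alike. Add that death within the first year excuses a subject from the one-year follow-up data requirement only, not from the surgery-date requirement. Naming the extraction date also gives the synopsis limit a fixed reference point, which it lacks.

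The cost is one sentence in each section and the loss of a few recent deaths: under the 5% assumptions, 0.07/5.07 = 1.4% of the data set with five eligible years, or about 4 in 300. No extra data or staff are needed. Early deaths after operations more than a year old stay in, so no opposite bias is created.

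This does not cure a separate problem. Section 5.3.1 drops survivors who lack one-year data while keeping deaths. If 10% to 20% of one-year survivors lack such data (assumed; true mortality 5% at 30 days and 10% at one year), the reported 30-day rate is 0.05/(0.10 + 0.90 × 0.90) = 5.5% to 0.05/(0.10 + 0.90 × 0.80) = 6.1%, even with the date limit in place. That needs its own correction.
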